Study Protocol and Statistical Analysis Plan NCT03854539 August 27, 2020

Protocol. Participants. Healthy male and female adult participants (ages 18+) will be recruited from the Arkansas Tech University psychology student test pool and may receive course credit for participating. Participants fill out a questionnaire screening for mental disorders and use of substances which interfere with accurate assessment of salivary alpha amylase. The questionnaire also includes items on age, ethnicity and gender. In both experiments participants will be randomly assigned to groups with stimulation order determined using a Latin square design. Protection of human subjects. The IRB protocol is under review. Women and minorities are included and their data will be analyzed in accordance with the described data analysis plan. Stimulation procedures. We will apply sham stimulation and tVNS using identical stimulation parameters with the exception of electrode placement. *Electrode Placement.* Participants in tVNS condition groups will receive stimulation via electrodes attached on the anterior and posterior ear at the concha, an area richly innervated with vagal fibers [10]. *Sham-stimulated* participants will be stimulated with identical stimulus parameters as the tVNS group with the electrodes placed on the helix region. The helix region of the ear is thought to be free of vagal or other cranial nerve fibers. *Non-stimulation* participants will receive no stimulation. In the nonstimulation condition electrodes will be applied randomly to one of the above locations without electrical stimulation. The purpose of this group is to control for the possibility that mild stimulation will increase arousal through non-vagal pathways. *Stimulation parameters.* In the first study, to establish a stimulation intensity effect curve, participants will receive 0.0, 0.25, 0.5, or 1.0mA stimulation either to the concha or helix region (sham stimulation). The stimulus will consist of trains of 30Hz, with 0.5mS pulse width. Trains will alternate 30 seconds on and 30 seconds off for five minutes. In a second study to determine the relative effects of intermittent vs constant stimulation, participants will receive helix (sham) or concha (tVNS) stimulation at the 0.5mA level. Intermittent stimulation will consist of trains of 30Hz, with 0.5mS pulse width. Trains will alternate 30 seconds on and 30 seconds off for ten minutes. Constant stimulation will be identical with the exception that instead of alternating on-off periods, the stimulation will be a single five minute on block (holds total number of impulses equal). *Salivary Alpha Amylase.* Saliva samples will be collected using the passive drool method, considered to be the superior method for collection of alpha amylase samples [11]. Participants allow drool to pool inside the oral cavity and use a straw to provide 2mL of saliva into a cryogenic sample container. Following collection samples are placed on ice and then frozen until assay. *Salivary alpha amylase assay.* Samples are assayed using kinetic reaction assay, without modifications to the manufacturer's recommended protocol (Salimetrics, State College, PA) will be used. Details on this assay can be found in Gordis *et al* [11]. For sAA, sample test volumes are 10 μ l and the lower limit of sensitivity is 0.4 U/mL. Samples are tested in duplicate with the average of the duplicates used for analysis. Duplicates exceeding 10% variance will be re-assayed. As a secondary measure, heart rate will be monitored by ECG and continuously recorded (3 lead) throughout the experiment using an iWorx TA device. Recoding electrodes are placed on the right and left clavicles and costal margin. Heart rate will be used to confirm sympathetic induction and effects of heart rate variability may later be investigated as a primary measure in future studies.

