
Data analysis Within-subject percent change from immediately preceding baseline scores will be calculated for each level of stimulation ([baseline/stimulation] *100). Statistical analysis of percent changes in salivary alpha amylase concentrations by stimulation group will be performed with one-way repeated measures ANOVA with Bonferroni correction for multiple comparisons of each stimulation level to the sham stimulation level. Statistical analysis to determine changes in baseline concentration of salivary alpha amylase within each intensity will be conducted using repeated measures ANOVA with Bonferroni correction for

multiple comparisons. A significance level of $p < 0.05$ will be used for all statistical tests conducted. Within-subject percent change from immediately preceding baseline scores will be calculated for each level of stimulation ($[\text{baseline}/\text{stimulation}] * 100$). Statistical analysis of percent changes in salivary alpha amylase concentrations by stimulation group will be performed with one-way repeated measures ANOVA with Bonferroni correction for multiple comparisons of each stimulation level to the sham stimulation level. Statistical analysis to determine changes in baseline concentration of salivary alpha amylase within each intensity will be conducted using repeated measures ANOVA with Bonferroni correction for multiple comparisons. A significance level of $p < 0.05$ will be used for all statistical tests conducted.

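### The alpha amylase outcome is called a percent change but is defined as baseline divided by stimulation, so a rise gives a lower score on a distorted scale

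*Combined protocol and SAP*

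**What the plan says.** The Data analysis section gives one definition of the outcome: "Within-subject percent change from immediately preceding baseline scores will be calculated for each level of stimulation ([baseline/stimulation] *100". The whole paragraph is printed twice, and baseline is in the numerator and stimulation in the denominator both times.

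The next sentence sends this score to the main test: "Statistical analysis of percent changes in salivary alpha amylase concentrations by stimulation group will be performed with one-way repeated measures ANOVA". In the same sentence, each level is to be compared against sham under a Bonferroni adjustment. A further repeated measures ANOVA, on baseline concentrations, does not use the score.

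Under Stimulation parameters, the aim of the first study is "to establish a stimulation intensity effect curve, participants will receive 0.0, 0.25, 0.5, or 1.0mA stimulation".

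The document never names alpha amylase as primary. That it is the main outcome is an inference, but a safe one: it is the only variable in the Data analysis section, and the Protocol introduces heart rate with the words "As a secondary measure, heart rate will be monitored by ECG".

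Nothing in the document gives another formula or says that a lower score means a rise.

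**The concern.** The label and the formula describe different variables. A percent change has a difference in the numerator and baseline in the denominator. The printed formula has no difference and divides by the stimulation value.

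Three things are at stake if it is followed as written:

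- **Direction.** An increase in alpha amylase, the response the stimulation is meant to be tested for, appears as a lower score.
- **Scale.** The score is not a linear function of percent change, so means, variances, p-values and the shape of an intensity curve all change. Relabelling the axis afterwards does not repair this.
- **Reproducibility.** One analyst could follow the label and another the formula. They could reach different significance calls, and each could claim to have followed the plan.

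**Working it through.** The plan states no sample size, SD or expected effect, so it has no figure to reproduce. The check evaluates the printed formula and compares it with the two variables that could have been meant.

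**1. The formula itself (no assumptions).** Let B be baseline, S the stimulation value and f = S/B.

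- As printed: 100 × B/S = 100/f
- Percent of baseline: 100 × S/B = 100f
- Percent change: 100 × (S − B)/B = 100(f − 1)

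| f | As printed | Percent of baseline | Percent change |
|---|---|---|---|
| 0.5 | 200 | 50 | −50 |
| 1 | 100 | 100 | 0 |
| 1.25 | 80 | 125 | +25 |
| 1.5 | 66.7 | 150 | +50 |
| 2 | 50 | 200 | +100 |

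Percent of baseline and percent change differ by the constant 100, so an ANOVA gives the same p-values for both. The printed score is 10,000 divided by percent of baseline. That is nonlinear, so its p-values generally differ.

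**2. The intensity curve (assumed effect).** Take the first study's levels of 0, 0.25, 0.5 and 1.0 mA and assume a straight-line rise of 0, 25, 50 and 100%. The printed scores are 100, 80, 66.7 and 50. The drop per 0.25 mA is:

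- 0 to 0.25 mA: 100 − 80 = 20
- 0.25 to 0.5 mA: 80 − 66.7 = 13.3
- 0.5 to 1.0 mA: (66.7 − 50)/2 = 8.3

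A linear effect is turned upside down and appears to level off.

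**3. Mean scores (assumed log-normal f, median rise 20%).** The mean printed score is 100 × exp(−ln 1.2 + s²/2), where s is the log SD. For s = 0.2, 0.4, 0.6 and 0.7 it is 85.0, 90.3, 99.8 and 106.5. At s = 0.6 a real rise averages to almost exactly the no-change value of 100. Mean percent of baseline in the same cases is 122.4, 130.0, 143.7 and 153.3: the right side of 100, though also inflated by skew.

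**4. Significance calls (simulation).** Assumptions: 40,000 data sets per setting; log ratios for active and sham independent and normal with equal SD s; active shifted by 0.8 × s; paired t-test at two-sided 5%. The table gives the percentage of data sets in which the printed score and true percent change disagree on p < 0.05.

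| n | s = 0.3 | s = 0.5 | s = 0.7 |
|---|---|---|---|
| 12 | 10.4 | 16.3 | 21.1 |
| 20 | 10.8 | 18.4 | 24.6 |
| 30 | 7.9 | 13.9 | 20.8 |

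Repeat runs with other random seeds agreed to within about 0.6 percentage points. At s = 0.1 and n = 20 the disagreement is under 4%.

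**5. Power.** With equal log SDs the two scores are mirror images, so average power is the same by construction: at n = 20 and s = 0.3, 65.7% for the printed score and 65.6% for percent change. With unequal SDs it is not. At n = 20, a log shift of 0.3, and log SD 0.5 for active and 0.3 for sham, power is about 40% for the printed score and 70% for percent change. With the SDs exchanged, the two powers change places.

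**The case against.** The strongest reply is that this is a slip of notation. The label shows the intent, the following sentence again speaks of percent changes, and an analyst might never apply the formula literally. The second printing looks like a pasted copy, so it is weak evidence of a deliberate choice. The document does not show what was computed, and the raw concentrations are unaffected. All of that is fair, and it makes the harm conditional on literal use. It does not remove the contradiction. The document offers no other formula, and swapping the two terms gives percent of baseline, which is still not what the label says.

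The simulation has real limits. SD, effect, sample size and independence of the two ratios are all assumed. It tests one unadjusted pair, not the planned ANOVA with Bonferroni correction. Part of the disagreement is ordinary sensitivity to scale: percent change and a log-ratio analysis disagree in 5.8%, 10.1% and 14.7% of the same data sets at n = 20 for log SD 0.3, 0.5 and 0.7. The figures show that the choice of formula can change a conclusion; they do not estimate error in this trial.

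The levelling-off also depends on an assumed straight-line effect, and the plan fits no curve or trend model. The bending would therefore affect how the curve is described rather than a planned trend test.

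**Conclusion.** The concern holds, and the definition must be corrected. As written, the plan specifies the wrong analysed variable for its main comparison. The inversion and the nonlinearity follow from the formula alone and need no assumptions: a 50% rise scores 66.7, a doubling 50 and a halving 200.

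The effect on significance depends on data the document does not describe. Under the stated assumptions, with log SD 0.3 to 0.7 and 12 to 30 participants, the written formula and true percent change give different calls in about 8% to 25% of data sets, and in fewer when the spread is small. Power can be lower or higher than for percent change when active and sham ratios differ in spread. The ANOVA on baseline concentrations is not affected.

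**What to change.** Replace the formula in both printings with 100 × (stimulation − baseline) / baseline, and state that a positive value means a rise. This matches the plan's own label. If the sponsor confirms that percent of baseline was meant, 100 × stimulation / baseline with a corrected label is equally acceptable and gives the same p-values. Delete the duplicate paragraph so that only one definition remains.

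Then check which formula the analysis code uses and recalculate any results obtained with the inverted one.

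A separate, optional improvement is to analyse log(stimulation/baseline) and report 100 × (ratio − 1)%. This deals with the skew of raw ratios and treats rises and falls symmetrically.

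The cost is one formula, a code check and, if needed, a rerun on the existing concentrations. No new samples or participants are required.

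### Intensity contrasts rest on a ratio to baseline with no covariate; adjusting log post-stimulation amylase for the same baseline is usually more precise

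*Combined protocol and SAP*

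**What the plan says.** The Data analysis section defines the outcome as a within-subject change: "percent change from immediately preceding baseline scores will be calculated for each level of stimulation". The model follows: "Statistical analysis of percent changes in salivary alpha amylase concentrations by stimulation group will be performed with one-way repeated measures ANOVA". Each level is then compared with sham, and those contrasts are Bonferroni-corrected. A 0.05 level "will be used for all statistical tests conducted". The section names no covariate and no log transform.

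A second analysis concerns the baselines themselves: "Statistical analysis to determine changes in baseline concentration of salivary alpha amylase within each intensity will be conducted using repeated measures ANOVA". That is a separate test and does not adjust the stimulation contrasts.

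On design, the Participants paragraph says that "participants will be randomly assigned to groups with stimulation order determined using a Latin square design". The Stimulation parameters paragraph lists four intensities for the first study (0.0, 0.25, 0.5 and 1.0 mA), applied to the concha or, as sham, to the helix. The documents give no sample size, SD, effect size or pre-post correlation.

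**The concern.** On the log scale, a ratio to baseline forces the slope of post-stimulation amylase on baseline to equal 1. If the true slope is below 1, part of what is subtracted is noise.

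The repeated measures model and Latin-square ordering suggest that intensities are compared within persons. Participant effects then already remove each person's usual amylase level, so the ratio is not needed for that purpose. What remains is session-to-session fluctuation, and the question is how much of it the baseline and post-stimulation samples share. That is the within-person correlation r, measured after participant and level effects are removed.

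At stake is the precision of the contrasts that make up the intensity-effect curve, which is the stated aim of the first study. The question is one of efficiency, not validity. The printed formula puts baseline over stimulation. That is a separate defect and is not counted here: the ratio below is stimulation over baseline.

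**Working it through.** The plan has no figure to reproduce. The inputs are as follows.

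- From the documents: four intensity levels, a 0.05 significance level and Bonferroni correction. Reading the contrasts as three active levels against one reference gives 0.05/3 = 0.0167 per contrast, taken as two-sided.
- Assumed: r, n, SDs and effect, as stated at each step.

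**Large-sample variance.** With equal pre and post log variances, in units of that variance, contrast variance is proportional to:

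- log ratio: 2(1−r)
- baseline-adjusted (ANCOVA): 1−r²
- baseline ignored: 1

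ANCOVA over log ratio is (1−r²)/[2(1−r)] = (1+r)/2. The log ratio is noisier than ignoring baseline when 2(1−r) > 1, that is, when r < 0.5.

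**Simulated power.** There are 10,000 crossover data sets per setting, with n = 20, four levels, within-person log SD 0.5, between-person log SD 0.8, effect 0.45 log units and alpha 0.05/3.

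| r | Variance, ANCOVA / log ratio | Ratio | Log ratio | ANCOVA | Baseline ignored |
|---|---|---|---|---|---|
| 0.2 | 0.60 | 42% | 42% | 66% | 65% |
| 0.5 | 0.75 | 67% | 65% | 78% | 65% |
| 0.7 | 0.85 | 91% | 89% | 93% | 65% |
| 0.9 | 0.95 | 100% | 100% | 100% | 65% |

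Per-comparison error under no effect (20,000 runs) was 1.5% to 1.8%, against a nominal 1.7%.

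**The same loss in participants.** Take another set of assumptions: within-person log SD 0.4, effect 0.35, 80% power. The normal approximation is n = 2V(0.16)(2.394+0.842)²/0.1225 = 27.35V, where V is the variance factor above.

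- r = 0.2: V = 1.60 against 0.96, so 44 participants for the log ratio and 27 for ANCOVA
- r = 0.5: V = 1.00 against 0.75, so 28 and 21
- r = 0.7: V = 0.60 against 0.51, so 17 and 14
- r = 0.9: V = 0.20 against 0.19, so 6 and 6

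**Where the gain disappears.**

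- Small n: at n = 8 the ratio has 15%, 27%, 46% and 93% power at the four values of r; ANCOVA has 24%, 31%, 46% and 90%.
- High r with a small effect: at n = 20, effect 0.2 and r = 0.9, the ratio has 67% and ANCOVA 65%.
- Break-even against the log ratio, allowing for the estimated slope and one lost degree of freedom: r = 0.82 at n = 6, 0.91 at n = 10 and 0.97 at n = 24.
- Unequal variances: with q = SD post / SD pre, the variance ratio is q²(1−r²)/(q²+1−2rq). At q = 1.25 and r = 0.8 this is 1.5625 × 0.36 / (1.5625+1−2) = 0.5625/0.5625 = 1.00.

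**If site is between persons, with one session each.** The total correlation applies: (0.64+0.25r)/0.89 = 0.78, 0.86 and 0.92 at r = 0.2, 0.5 and 0.7. The variance ratio is then only 0.89, 0.93 and 0.96.

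**Carryover.** Suppose half the top level's effect carries into the next session of a carryover-balanced four-sequence square. The reference level follows the top level in one sequence of four, and the top level never follows itself. The imbalance is 0.5 × 1/4 = 12.5% of the effect. Simulated bias (20,000 runs, n = 20), as a percentage of the effect:

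| Carryover | Log ratio | ANCOVA, r = 0.2 / 0.5 / 0.7 / 0.9 |
|---|---|---|
| Persists through the post sample | about 0 | −9.5 / −5.9 / −3.4 / −1.0 |
| Affects the baseline only | about +12.6 | +2.2 / +6.2 / +8.4 / +10.8 |

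**The case against.** The strongest reply is that no material loss is shown for this trial. Baseline immediately precedes stimulation, and stimulation in the first study lasts five minutes, so r could be high. At r = 0.7 or above the methods are nearly level. This stands as a limit on size. It does not favour the ratio, because when r is unknown, estimating the slope protects against a low value and costs little at a high one.

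Second, the comparator is unclear. Sham is defined as helix placement, so the planned contrast may be concha against helix rather than active levels against 0.0 mA, and the references to groups could make site a between-person factor. The power table does not apply to that case, and no lost power is claimed for it. The direction is unchanged, since in large samples an estimated slope is never less precise than a fixed one.

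Third, at r = 0.2 nearly all the gain comes from not dividing by baseline: 66% for ANCOVA against 65% for ignoring it. That is correct. Adjustment itself adds most in the middle of the range.

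Fourth, baselines after the first are post-randomisation. Under persistent carryover the ratio is unbiased and ANCOVA is not, most of all at low r, where its precision gain is largest. This is a real trade-off, but the ranking reverses if carryover reaches only the baseline, and the planned ratio depends on the same baselines.

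**Conclusion.** The concern holds as a point of efficiency. The plan fixes the baseline slope at 1 where it could be estimated from data already being collected.

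At n = 20 under the stated assumptions, the cost against the correctly oriented ratio is 24 percentage points of power at r = 0.2 (66−42), 11 at r = 0.5 (78−67), 2 at r = 0.7 (93−91) and none at r = 0.9. These sizes rest on an assumed n, SD, effect and r, and on intensities being compared within persons. The loss can be nil or slightly reversed when n is very small, r is very high, or the true slope is close to 1. Without carryover both analyses are valid; under carryover neither is always the less biased. The change should be made, with medium confidence in how much it matters here.

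**What to change.** Make the main analysis a repeated measures model of log post-stimulation alpha amylase, with participant effects, stimulation level and the immediately preceding log baseline as a within-person covariate. Report geometric mean ratios, expressed as percent differences. Keep percent change for description and the log ratio as a sensitivity analysis. Interpret the result alongside the planned analysis of baseline changes, which speaks to carryover.

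State which condition is the sham comparator and whether site is a within-person or between-person factor. If it is between persons, adjust that contrast for the first, pre-stimulation baseline. A participant's mean baseline would include values taken after stimulation had begun.

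The cost is SAP wording, a log transform, one model term and one degree of freedom. The estimand becomes an adjusted geometric mean ratio instead of a mean percent change. No new samples or participants are needed.

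### Study 1 has a helix sham at each active current, but the analysis compares every level with one unspecified sham level, with no site term or same-current contrast

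*Combined protocol and SAP*

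**What the plan says.** **Conditions.** Under Stimulation parameters, Study 1 "participants will receive 0.0, 0.25, 0.5, or 1.0mA stimulation either to the concha or helix region (sham stimulation"). Under Stimulation procedures, "We will apply sham stimulation and tVNS using identical stimulation parameters with the exception of electrode placement". Electrode Placement adds that sham "participants will be stimulated with identical stimulus parameters as the tVNS group with the electrodes placed on the helix region". Sham is therefore a placement, and it exists at each of the three active currents.

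**No-stimulation control.** This is described apart from sham: "In the nonstimulation condition electrodes will be applied randomly to one of the above locations without electrical stimulation". The reason given is "The purpose of this group is to control for the possibility that mild stimulation will increase arousal through non-vagal pathways".

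**Allocation.** Under Participants, "participants will be randomly assigned to groups with stimulation order determined using a Latin square design".

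**Analysis.** The Data analysis section calls for a "one-way repeated measures ANOVA with Bonferroni correction for multiple comparisons of each stimulation level to the sham stimulation level", applied to percent change in salivary alpha amylase by stimulation group. A second analysis looks at shifts in baseline within each intensity and does not compare sites. The section's text appears twice, and neither copy says more about the comparator.

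**The concern.** The design isolates the vagal effect by holding every stimulus parameter fixed and moving only the electrode. Only a comparison of concha with helix at the same current makes use of that. The analysis text refers to one sham level in the singular, while the design supplies three. An analyst could take 0 mA, one helix intensity, the pooled helix conditions or the matched helix condition, and nothing in the plan prevents choosing after the data are seen.

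If stimulation causes arousal that has nothing to do with the vagus and grows with current, any single comparator counts part of it as a tVNS effect at high current, hides a real effect at low current, or does both. Study 1 is meant to describe how the effect changes with intensity, so an error that grows with current falls on its main result.

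The plan also leaves open whether site varies between or within participants. Assignment to groups suggests between; an order set by Latin square suggests that at least intensity varies within. If site is between participants, a one-way repeated measures model has no place for it.

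**Working it through.** The documents give no sample size, SD or effect size, so there is no planned figure to reproduce. The only stated input to the tests is the 0.05 significance level.

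**1. Cells and comparisons.** Active cells: 3 currents × 2 sites = 6. Adding 0 mA gives 7 cells, or 8 if 0 mA is split by site. The number of Bonferroni comparisons depends on the reading:
- three concha levels against sham: 0.05/3 = 0.0167 per test
- every other cell of 7 against one sham cell: 0.05/6 = 0.0083
- every other cell of 8: 0.05/7 = 0.0071

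**2. Bias, which needs no n or SD.** Assume no vagal effect and non-vagal arousal that is linear in current, equal at both sites and of size A at 1.0 mA. Signs refer to a response that rises with arousal.

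Apparent tVNS effect = (concha current − mean comparator current) × A

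Mean current of the pooled active helix conditions = (0.25 + 0.5 + 1.0)/3 = 0.583 mA.

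| Comparator | Concha 0.25 mA | Concha 0.5 mA | Concha 1.0 mA |
|---|---|---|---|
| 0 mA | +0.25A | +0.50A | +1.00A |
| Helix 0.5 mA | −0.25A | 0 | +0.50A |
| Pooled active helix | −0.33A | −0.08A | +0.42A |
| Helix at the same current | 0 | 0 | 0 |

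**3. False-finding rates (illustration).** Assumed inputs: 20 participants per site, within-subject SD 1, between-subject SD 0.5, an additive normal response, three two-sided t tests at 0.05/3, no vagal effect, 20,000 replicates. A is in units of the within-subject SD. Entries are the chance of at least one significant concha-versus-sham result.

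| Layout and comparator | A = 0 | 0.25 | 0.5 | 1.0 |
|---|---|---|---|---|
| Site between: 0 mA (paired) | 5% | 8% | 21% | 72% |
| Site between: helix 0.5 mA | 4% | 5% | 8% | 20% |
| Site between: pooled helix | 4% | 6% | 9% | 24% |
| Site between: matched | 5% | 5% | 5% | 5% |
| All within: 0 mA | 5% | 8% | 21% | 72% |
| All within: pooled helix | 5% | 6% | 10% | 31% |
| All within: matched | 5% | 5% | 5% | 5% |

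These reproduce to within about one percentage point on repetition. With site between participants and A = 1.0:
- *Direction.* The 24% for pooled helix splits into 14% finding concha above sham and 10% finding it below. The 72% is nearly all concha above.
- *Sample size.* With 15 per site the rates are 56% (0 mA), 18% (pooled helix) and 5% (matched). With 30 per site they are 91%, 37% and 5%. A larger sample makes the single-comparator error worse.

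**4. Check of the remedy.** Three independent tests at 0.0167 give 1 − (1 − 0.0167)³ = 0.049. A random-intercept model with a shared 0 mA cell (4,000 replicates, 20 per site) gave a family-wise error for the matched contrasts of 4.8% at A = 0 and 4.9% at A = 1.0.

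**The case against.** The strongest reply is that the protocol defines sham as helix stimulation with the same parameters as tVNS, so the sham for a given level is naturally helix at that level. On that reading the comparison is sound. The stimulation group analysed could also be a composite of site and current, and a one-way model over such cells is legitimate if every participant receives all of them. Both readings are reasonable. The text states neither, and a composite factor still leaves one comparator in the singular. What stands is that the plan fails to specify a matched analysis; it does not clearly commit to a mismatched one.

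The numbers also have limits:
- The 72% treats 0 mA as the sham level, although the protocol describes no-stimulation separately from sham. It also pairs 0 mA within the concha participants; with a separate 0 mA group it falls to about 64%. It is a worst case.
- Arousal of one full within-subject SD has no support in the documents. With site between participants and A at 0.5 SD or less, helix at 0.5 mA and pooled helix give 4% to 9%, close to nominal.
- The simulation uses t tests on an additive response, not the planned ANOVA on a ratio of baseline to stimulation values.

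These points limit how far the error rates can be pressed. They do not affect the bias arithmetic under its stated assumptions, or the gap in the text.

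Finally, the stated aim is an intensity curve rather than site contrasts. The two are compatible: the three same-current contrasts, set against current, are the sham-corrected curve.

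**Conclusion.** The concern holds and should be settled before the data are analysed, because it concerns the plan's only test of stimulation against sham. The comparator is unspecified, site is not named in the model, and no same-current contrast is named.

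That finding rests on the text alone. The size of the harm is conditional on non-vagal arousal that rises with current. For linear, site-independent arousal, the spurious effect at 1.0 mA is 42% to 100% of A for the three single comparators tabulated, and zero with matched contrasts. Under the assumed n and SDs, the family-wise false-finding rate at A = 1.0 SD is 20% to 31% for the helix comparators tabulated and up to 72% for 0 mA, against about 5% when matched. Without such arousal every reading stays near 5%.

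**What to change.** 1. State whether site varies between or within participants in Study 1.
2. Name three key contrasts: concha minus helix at 0.25, at 0.5 and at 1.0 mA, with Bonferroni or Holm adjustment over the three.
3. Fit a mixed model with 2 sites × 3 active currents plus one shared 0 mA cell and a random participant effect, with site entered as it was randomised. If every participant receives all cells, a one-way cell-means repeated measures model with the same named contrasts also serves.
4. Name helix versus 0 mA as the check for non-vagal arousal, which is the purpose the protocol gives the no-stimulation control.
5. Report the intensity trend by site as a description of the curve.

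**Cost.** SAP wording and a standard model; the conditions and samples stay as planned. If site is between participants, matched contrasts are less precise than paired ones. With within-subject SD 1, the standard error is larger by √(1 + between-subject variance): √1.25 = 1.12 at a between-subject SD of 0.5, and √2 = 1.41 at 1.0. Since no sample size is given, whether the study is large enough for these contrasts cannot be judged from the documents.

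### Holm's step-down procedure could replace single-step Bonferroni at the same 5% family-wise error, with more power for the second and later stimulation levels: an optional improvement, not an error

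*Combined protocol and SAP*

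**What the plan says.** In the Data analysis section, percent change in salivary alpha amylase by stimulation group "will be performed with one-way repeated measures ANOVA", followed by "Bonferroni correction for multiple comparisons of each stimulation level to the sham stimulation level". A second repeated measures ANOVA, on changes in baseline concentration within each intensity, also carries a Bonferroni correction. The section closes with "A significance level of $p < 0.05$ will be used for all statistical tests conducted". The whole text is printed twice, so each of the two corrections appears twice. No step-down method and no confidence intervals are mentioned.

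Under Stimulation parameters, the first study is meant "to establish a stimulation intensity effect curve", and "participants will receive 0.0, 0.25, 0.5, or 1.0mA stimulation either to the concha or helix region (sham stimulation". In the second study, which compares intermittent with constant stimulation, "participants will receive helix (sham) or concha (tVNS) stimulation at the 0.5mA level". The documents do not state how many comparisons each correction covers. They also give no sample size, power target, SD or expected effect.

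**The concern.** Single-step Bonferroni tests every level at 0.05/m, where m is the number of comparisons in the family, whatever the other levels show. Once one hypothesis has been rejected, at most m−1 true null hypotheses can remain, and a threshold of 0.05/(m−1) is enough to protect them. Holm's procedure uses this; single-step Bonferroni does not.

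What is at stake is power for the second and later levels in a study that compares several intensities with sham. One might keep single-step Bonferroni because it yields simultaneous confidence intervals directly, but this plan asks for none.

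**Working it through.** **Inputs.** From the documents: significance level 0.05 (taken as two-sided, since no sidedness is given), Bonferroni correction, each level against sham. Assumed, because the documents are silent: m=3 for the first study (0.25, 0.5 and 1.0 mA against sham), or m=4 if 0.0 mA counts as a level; m=2 for the second study (intermittent and constant against sham); all sample sizes, SDs and effects. The plan states no figure that could be reproduced.

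**1. Thresholds.** Bonferroni compares every p-value with 0.05/m. Holm orders the p-values and compares them with 0.05/m, 0.05/(m−1), ..., 0.05, stopping at the first that fails.

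| m | Bonferroni | Holm |
|---|---|---|
| 2 | 0.025 for both | 0.025, 0.05 |
| 3 | 0.0167 for all | 0.0167, 0.025, 0.05 |
| 4 | 0.0125 for all | 0.0125, 0.0167, 0.025, 0.05 |

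**2. What follows without simulation.**

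- No Holm threshold lies below 0.05/m, so Holm rejects everything that Bonferroni rejects.
- The first step is the same in both, so the chance of at least one rejection is identical.
- Suppose m₀ hypotheses are truly null. The first of them that Holm reaches stands at rank m−m₀+1 or earlier, so its threshold is at most 0.05/m₀. By the Bonferroni inequality over the m₀ nulls, the family-wise error is at most m₀ × 0.05/m₀ = 0.05 under any dependence.
- With all nulls true and independent tests, both procedures have error 1−(1−0.05/m)^m: 0.0494 for m=2, 0.0492 for m=3 and 0.0491 for m=4.

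**3. Illustration with paired t tests.** Assumptions: three levels against one shared sham condition in the same participants, independent errors with SD 1 per condition, and at least 20,000 simulated trials per row. The Monte Carlo standard error is at most √(0.25/20,000) = 0.35 points. An effect of 0.8 SD at n=30 gives a noncentrality of 0.8 × √30/√2 = 3.10.

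| n | True effects (SD) | Result | Bonferroni | Holm |
|---|---|---|---|---|
| 30 | 0.8/0.8/0.8 | power per comparison | 71% | 79% |
| 30 | 0.8/0.8/0.8 | all three detected | 47% | 67% |
| 30 | 0.8/0.8/0.8 | at least one detected | 91% | 91% |
| 40 | 0.6/0.6/0.6 | power per comparison | 57% | 66% |
| 40 | 0.6/0.6/0.6 | all three detected | 32% | 50% |
| 30 | 0.3/0.6/0.9 | power at each level | 10%, 42%, 82% | 18%, 49%, 83% |
| 30 | 0/0/0.8 | power for the one real effect | 71% | 71% |
| 30 | 0/0/0 | family-wise error | 4.6% | 4.6% |

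With effects of 0.1/0.3/0.8 SD at n=30, the gains at the three levels are about 2, 3 and 0 points. If each level has its own helix sham instead of a shared one, the chance of detecting all three at n=30 and 0.8 SD goes from 36% to 60%.

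**4. Second setup.** Here z tests were used, each real effect was sized for 80% power at 0.05/m, and the test statistics had correlation 0 or 0.5 (400,000 simulated trials).

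- With m=3, correlation 0.5 and all effects real, average power rises from 80.0% to 86.4%, the chance of all three from 61.1% to 76.6%, and at least one stays at 94.9%.
- Over the two correlations, the gain in average power with all effects real is 4.6 to 5.5 points for m=2, 6.4 to 8.0 for m=3 and 7.5 to 9.4 for m=4.
- With only one real effect the gain is about 0.1 to 0.2 points.
- With m=3, two real effects and correlation 0.5, the realised error on the remaining null is 0.017 under Bonferroni and 0.039 under Holm.

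**The case against.** The strongest case against raising this is that nothing in the plan is wrong. Bonferroni is prespecified, valid and conservative, and it causes no bias, excess false positives or contradiction. Choosing between two valid procedures can fairly be called a preference. This stands, and it is why the point is offered only as an improvement.

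Three further objections also stand in part:

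- **The benefit cannot be sized for this trial.** The number of comparisons, sample size, SD and effects are all missing. A shared sham is itself doubtful, because the Stimulation parameters text allows helix stimulation at any of the listed intensities, which could mean an intensity-matched sham. The direction of the gain does not depend on these inputs, but its size does.
- **Holm spends more of the permitted error.** When some levels work and others do not, its realised error is higher (0.039 against 0.017 above). That remains inside the 5% limit that the plan itself sets.
- **Simultaneous confidence intervals.** Holm has no simple matching set. Since none are planned, no planned output is lost. If they were wanted later, this would be a real cost.

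Two stronger readings are tempting, and the documents support neither. A reader might infer that Bonferroni flattens the lower part of the intensity curve. A multiplicity adjustment changes which levels are called significant. It does not change the estimated mean at any level. A reader might also infer that the first study succeeds only if every intensity is shown to differ from sham. The stated aim is to establish an effect curve, and detection at all levels is nowhere made a criterion, so the rise from 47% to 67% is not the trial's probability of success.

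**Conclusion.** The point holds as a low-priority, nearly free improvement. Three facts need no assumption about this trial: Holm has the same 5% family-wise limit under any dependence, never rejects fewer hypotheses, and leaves the chance of at least one rejection unchanged.

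The size does rest on assumptions. It is about 8 points of per-comparison power (71% to 79%) in a favourable case with three equal effects, and 0 to 3 points when the lower levels have small effects (0.1/0.3/0.8 SD). It is practically nothing when a single level works. It would be wrong to infer from this that the planned analysis is invalid or that its conclusions would be unreliable.

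**What to change.** Before the data are analysed, replace Bonferroni with *Holm step-down Bonferroni* wherever the Data analysis section prescribes the correction: for the comparisons with sham and for the baseline-change comparisons, in both printed copies of the text.

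Define each family first. For each study and each of the two analyses, state which comparisons belong and hence what m is, including whether 0.0 mA counts as a level. The number three should not be written in without that decision.

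Within a family, order the p-values as p₍₁₎ ≤ ... ≤ p₍ₘ₎, compare them with 0.05/m, 0.05/(m−1), ..., 0.05, and stop at the first that is not significant. Report the Holm-adjusted p-value for rank k, which is the largest value of (m−j+1) × p₍ⱼ₎ over j ≤ k, capped at 1. It is read directly against the plan's 0.05.

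The cost is a wording change and a software option, with no effect on procedures, samples or participants. The change should not be made after results have been seen. If simultaneous confidence intervals are to be reported after all, say so and specify a method for them separately.
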